2 SUBJECT SELECTION

2.1 DIAGNOSIS CRITERIA

According to the guidelines for the diagnosis of idiopathic pulmonary fibrosis 2018 edition, the diagnosis of IPF needs to meet the following criteria:

- (1) Ruling out other ILD with known reasons (such as exposure in living and working environments, connective tissue diseases and drugs), with the following second or third performance
- (2) HRCT images with UIP features
- (3) Meeting specific combinations of HRCT features and pulmonary pathology features for patients with lung disease.

2.2 INCLUSION CRITERIA

- (1) Male or female, aged between 50 to 75;
- (2) Subjects diagnosed with IPF according to guidelines for the diagnosis of idiopathic pulmonary fibrosis 2018 edition;
- (3) Subjects with 30%~79% of the predicted value in diffusing capacity for carbon monoxide (DLCO) and more than 50% of the predicted value in forced vital capacity (FVC) in pulmonary function tests 3 months before screening;
- (4) Subjects with typical High-resolution computed tomography (HR-CT) imaging findings of idiopathic pulmonary fibrosis in the past 12 months;
- (5) Subjects tolerant to bronchofiberscope;
- (6) Subjects fully informed of the purpose, method and possible discomfort of the trial, agreeing to participate in the test, and voluntarily signing the informed consent;
- (7) Subjects with good adherence, willingness to take medication and regular follow-up examinations as required by the protocol ;
- (8) Subjects able to understand and cooperate with the completion of pulmonary function tests.

2.3 EXCLUSION CRITERIA

- (1) Subjects who cannot tolerate cell therapy
- (2) Pregnant or lactating women;
- (3) Subjects with syphilis or any of human immunodeficiency virus (HIV), hepatitis B virus (HBV), hepatitis C virus (HCV) positive antibody; Of which stable HBV carriers after drug treatment (DNA titer ≤ 500 IU/mL or copy number < 1000 copies/mL) and cured hepatitis C patients (HCV RNA is negative) can be enrolled;
- (4) Subjects with malignant tumors or a history of malignant tumors;
- (5) Subjects with taking drugs which caused lung fibroblast such as amiodarone in a long term before screening;
- (6) Subjects with infections in lung or other site, including bacterial and viral infections, requiring intravenous treatment before cell transplantation;
- (7) Subjects with a history of invasive or noninvasive mechanical ventilation within 4 weeks;
- (8) Subjects with any of the following lung diseases: asthma, active tuberculosis, pulmonary embolism, pneumothorax, pulmonary hypertension, pneumoconiosis, etc.; lung cancer, bronchiolitis obliterans or other active lung

- disease; Pneumonia currently or within the last 4 weeks;
Pneumonectomy Previously;
- (9) Subjects needing oxygen therapy currently (oxygen therapy time > 15h/d);
- (10) Subjects suffering from serious other systemic diseases, such as myocardial infarction, unstable angina, liver cirrhosis, acute glomerulonephritis, connective tissue disease, etc.;
- (11) Subjects with following results: leukopenia (leukopenia < $4 \times 10^9/L$) or agranulocytosis (leukocyte < $1.5 \times 10^9/L$ or neutrophils < $0.5 \times 10^9/L$) of any cause;
Blood creatinine > 2.5 times the upper limit of normal;
Alanine transaminase (ALT) and Aspartate transaminase (AST) > 2.5 times the upper limit of normal values in the laboratory tests.
- (12) Subjects with a history of mental illness or suicide risk, epilepsy or other central nervous system disorders
- (13) Subjects with severe arrhythmias (such as ventricular tachycardia, frequent supraventricular tachycardia, atrial fibrillation, atrial flutter, etc.) or atrioventricular block of degree II or above, shown by 12-lead Electrocardiogram (ECG);
- (14) Subjects with a history of abusing alcohol and illicit drug;

- (15) Subjects who are allergic to cattle products;
- (16) Subjects who participated in other clinical trials in the past 3 months;
- (17) Subjects with poor compliance and difficult to complete the investigation;
- (18) Investigators, employees of research centers or family members of them (none of whom are suitable to participate in the trial to ensure the objectivity of the research);
- (19) Subjects who had an acute IPF exacerbation or hospitalized for other respiratory diseases 3 or more times in the past 1 year;
- (20) Subjects who take nintedanib for medication within 1 month, or plan to continue taking nintedanib for medication;
- (21) Subjects with other acquired or congenital immunodeficiency disorders, or with a history of organ transplantation or cell transplant therapy;
- (22) Subjects whose expected survival may be less than one year judged by the investigator;
- (23) Male participants of childbearing potential and female participants within childbearing age were reluctant to use effective contraception from the time of signing the informed consent to 6 months after cell therapy;

- (24) Subjects assessed as inappropriate to participate in this clinical trial by investigator.

2.4 WITHDRAW CRITERIA

2.4.1 WITHDRAW DECIDED BY INVESTIGATOR

- (1) Patients with bad adherence, impacting the safety and tolerance evaluation;
- (2) Patients undergo adverse events, making the investigator believe further study is not suitable;
- (3) Other situations of the patient making the investigator believe further study is not suitable.

2.4.2 WITHDRAW DECIDED BY PATIENT

- (1) Patients have the right to withdraw for any reason;
- (2) Even though the patient has not officially withdrawn, follow-up, cell administration, or examinations were not conducted successfully as required by the protocol.

If the patient withdraws before finishing the study, the withdraw reason should be recorded in CRF and original note.

3 THE TESTED DRUG IN EXPERIMENT GROUP

3.1 NAME

Name: REGEND001 autologous therapy product (REGEND001 is a commercial cell produced by expanded human bronchial basal cells)

Dose: 0.6×10^6 /Kg/person- 3.3×10^6 /Kg/person

3.2 DRUG APPLICATION METHOD

3.2.1 THE COLLECTION, ISOLATION, AND EXPANSION OF REGEND001 CELLS BEFORE TREATMENT

Based on CT images, two healthy lung segments between 3-5th level bronchi were identified, from where tissue specimens were collected through bronchoscopy. The sample brush (with a trace amounts of bronchial tissues) was put in a sterile tube, and transported to Jiangxi Xlotus Medical Science and Technology Co., Ltd for isolation of bronchia basal cells. The tissue sample was collected by PBS washing and prepared single-cell suspension by enzyme digestion for cell culture. The basal cell culture system is a patented technology granted by Regend Therapeutics to Jiangxi Xlotus Medical Science and Technology Co., Ltd, including a combination of special growth factors and composite material for mimicking basal layer environment in vitro, so bronchial basal cells can be expanded selectively while other mature epithelial cells and fibroblasts

apoptosis by nature because they can't grow. After the expansion of bronchial basal cells for a certain period, it can be stored in liquid nitrogen as cell bank for a long term. Before the application to the patients, REGEND001 cells need to undergo a series of strict tests.

3.2.4 THE DETAILED PROCEDURE OF REGEND001 CELL THERAPY

The key steps for the transplantation of REGEND001 autologous therapy product:

- (1) The site of infusion includes middle lobe of right lung, lingula of left lung, basal segments in the lower lobes of both lungs. The upper lobes of both lungs are not infused;
- (2) Infuse REGEND001 cells to each lung segments through bronchofiberscope, with 3 ml at each segment;
- (3) Taking 3 ml of infusion product with 10 ml syringe, with 5 ml air inside to push infusion product to the distal lung at the speed of 4-6 s/ml;
- (4) The cells take around 1.5 hours to establish close adhesion with the inflammatory and injured lung area. After transplantation, patients were required to assume a supine position for 2 hours;
- (5) The patients are prohibited from eating and drinking for 2 hours, minimizing coughing and oral codeine is given if necessary.

3.3 TREATMENT COURSE

REGEND001 autologous therapy product is planned for one administration, and the treatment is divided into two stages. First, the collection, isolation and expansion of bronchial basal cells; second, the transplantation of REGEND001 autologous therapy. The whole procedure takes around 4 to 8 weeks. After that, the patients will be followed up for 24 weeks. The patients need to undergo corresponding examinations at hospital, including safety examination and efficacy examination.

3.4 CONCOMITANT MEDICATION

IPF drugs used by the patients, except nintedanib, are compatible with this clinical trial. The details of all concomitant medications should be recorded on the Concomitant Drug Use page of the Case Report Form, clarifying the reason for medication/treatment, administration/treatment methods, and start and end dates.

List of common IPF drugs used in clinic:

No.	Drug	Recommended dose	Main effect	Note
1	Pirfenidone	600~1800mg/d	Antiinflammation, antifibrosis, antioxidant	
2	Omeprazole	20~60mg/d	Treating gastroesophageal reflux disease associated with IPF	
3	N-Acetyl Cysteine	2~12mL/d	Antioxidants, relieve coughing	
4	Methylprednisolon	500~1000mg/d	Acute IPF exacerbation, hormone	
5	Prednisolone	≥1mg/kg/d	Acute IPF exacerbation, hormone	

List of other compatible concomitant drugs in this clinical trial:

No	Drug	Recommended	Main effect	Note
1	Moxifloxacin	400~800mg/d	Treating respiratory tract	
2	Eucalyptol, limonene and pinene enteric soft	600~1200mg/d	An expectorant that can dissolve the mucus	
3	Compound methoxyphenaine capsule	3~6 capsules/d	antispasmodic	
4	Prednisolone	10~60mg/d	Anti-inflammation, anti-allergy	
5	Alprazolam		Improve sleeping	

3.5 PACKAGING AND LABELING

3.5.1 PACKAGING SPECIFICATIONS

14 mL per package (Prior to product release, the required dosage is prepared directly in the production area, for example, 3 bags totaling 42 ml).

3.5.2 PACKAGING REQUIREMENTS

The product will be packaged in sealed sterile bags.

3.5.3 LABELS

- a. Inner packaging label
8cm×6cm

3.6 CELL ALLOCATION

The cells will be strictly used for autologous treatment. Once the cells are prepared, they will be immediately transported to the clinical facility by a designated individual and received by responsible personnel. The cells will be used by the managing physician of the subject.

3.7 PRODUCT STORAGE AND APPLICATION

Storage conditions: 2-8°C

Cell Administration: REGEND001 autologous cell suspension is delivered into the distal airways using a fiberoptic bronchoscope.

3.8 DRUG MANAGEMENT

A designated individual will be responsible for managing the cells. The cells will be counted after each use, and any unused cells and packaging will be collected and returned.

3.9 CODE ESTABLISHMENT

The patient identification number will be consistent with the cell preparation number. The numbering will start from the

patient's admission to the hospital, and all related documents will use the same numbering system.

3.10 QUALITY ASSURANCE MEASURES FOR REGEND001 CELL TRANSPORTATION

(1) First, ensure that the real-time temperature recorder is in good condition (with sufficient battery and calibrated within the past year). Set the temperature alarm upper limit to 8.1°C and the lower limit to 1.9°C.

(2) The packaged REGEND001 autologous therapy product, including both primary and secondary packaging, should be placed in a temperature-controlled box equilibrated at 2-8°C for transportation. Install an opened real-time temperature recorder inside the temperature-controlled box to monitor the temperature throughout the journey. Set the recording interval of the temperature recorder to 15 minutes, ensuring uninterrupted temperature monitoring, continuous recording, data storage, and alarms for temperature deviations. If air transportation restricts the use of temperature recorders, confirm the temperature during transportation using corresponding temperature indicator strips.

(3) Upon arrival of the REGEND001 autologous therapy at the clinical institution, personnel should inspect the

integrity of the packaging and confirm that the temperature displayed on the temperature recorder or indicated by the temperature indicator strip is within 2-8°C. Transport personnel should promptly remove the temperature recorder to verify the temperature inside the temperature-controlled box throughout the transportation process and complete the relevant documentation.

4 CONTROL GROUP

The control group is not involved in the early trial.

5 STUDY PROCEDURES

All subjects must sign an informed consent form prior to screening.

The study physician will provide the subjects with complete and truthful information about the background, objectives, trial design, direct and indirect benefits that the subjects can obtain, potential risks, and any other relevant information related to this clinical trial, in a quiet and private environment. The subjects will be allowed to think independently and discuss with the physician, ask any questions they have, and receive help to fully understand all the information. After the subjects make a voluntary decision

to participate, they and the study physician will sign the informed consent form simultaneously.

Please refer to the clinical trial flowchart at the beginning of the protocol for details on the specific study procedures.

5.1 FIBEROPTIC BRONCHOSCOPY EXAMINATION

- (1) Preoperative preparation: The patient's medical history, physical examination, CT examination, and laboratory tests should be thoroughly evaluated. The purpose and significance of the examination should be explained to the patient to eliminate any concerns. The patient should fast for at least 4 hours before the bronchoscopic procedure. Sedatives can be administered to those who are more anxious.
- (2) Local anesthesia: 2% lidocaine spray anesthesia is used in combination with inhalation anesthesia until there is a sense of obstruction in the throat.
- (3) Procedure steps: The patient is typically placed in a supine position, and the bronchoscope is inserted through the nostril. During the examination, the tracheal mucosal folds and cartilage rings should be observed for clarity. The mucosa of the bronchial tube should be smooth and the color normal, with no new growths,

ulcers, or bleeding points. The nature of any secretions and the sharpness of the interstitium should also be noted, and detailed records should be kept.

(4) Specimen collection: If there are any new growths, bronchoscopic biopsies should be performed.

(5) Postoperative: The patient should fast for 3 hours, and food and water should only be consumed after the anesthesia has worn off to avoid aspiration. The patient should be informed that there may be blood in their sputum post-procedure. If the patient develops a fever, antibiotic treatment should be administered. Oxygen should be administered to patients who experience shortness of breath or hypoxemia.

5.2 MANAGEMENT OF INELIGIBLE SUBJECTS DURING CELL CULTURING

In the time interval between subject enrollment and cell treatment (usually 4-8 weeks), if a subject who initially met the inclusion criteria becomes unsuitable for cell therapy (e.g., acute exacerbation of the condition, occurrence of severe complications), the subject's physical condition will be assessed by the researchers. If it is anticipated that the subject's condition can meet the standards for receiving cell transplantation after relevant interventions and observations, the cell therapy preparation work will be temporarily suspended. In such cases, there is no need to obtain new

cells, and the cells that have already been cultured or partially cultured will be cryopreserved according to the relevant regulations of the production facility. Once the subject is medically cleared, they can directly proceed to the trial, reschedule the treatment time, and use the cells for treatment after cell recovery, culturing, and testing. If, based on the researcher's assessment, the subject is deemed unsuitable to continue participating in the study (such as an anticipated lack of short-term improvement in the physical condition), the subject will be considered a screening failure, and their cells will be destroyed. Before the completion of the entire study, a subject can undergo a maximum of two baseline assessments to verify the inclusion criteria. If the subject fails to meet the criteria for cell therapy during the second baseline assessment, the subject will be withdrawn from the trial, and the cells will be destroyed or cryopreserved for long-term storage if requested by the subject. If, until the end of the study, the subject is unable to meet the inclusion criteria, the subject will be withdrawn from the study, and the cells will be destroyed or cryopreserved for long-term storage if requested by the subject.

Considerations regarding the standards or scope of pre-treatment examinations for subjects undergoing cell therapy primarily involve the researcher's further verification of the inclusion criteria. If the subject still meets the selection

criteria and does not meet any exclusion criteria, and there are no special circumstances, the researcher will assess and determine that the subject is still suitable for receiving cell therapy, and the treatment will proceed as planned. If the subject does not meet the inclusion criteria or meets any exclusion criteria, the treatment will be temporarily suspended (with the already cultured cells cryopreserved for later treatment), for example, the subject's condition has made significant progress: the increased risk of bronchoscopy due to worsening pulmonary inflammation, a follow-up CT scan (due to disease requirements or treatment interval exceeding 8 weeks) reveals concurrent lung cancer with a life expectancy of less than 1 year and posing a high risk of frequent acute exacerbations after expected cell therapy. In such complex situations, after comprehensive evaluation, the researcher deems the subject unsuitable for receiving cell therapy, and these circumstances can be considered as unacceptable treatment criteria or scope.

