1.4 STUDY PROCEDURE

This study includes screening stage V1, cell collection stage V2, baseline stage V3 (0-5 days before cell transplantation), REGEND001 autologous therapy product transplantation stage V4, follow-up stage V5-V9, safety follow-up stage after research. Follow-up stage includes: V5 (24 hours \pm 4 hours after transplantation), V6 (1 week \pm 2 days after transplantation), V7 (4 weeks \pm 3 days after transplantation), V8 (12 weeks \pm 5 days after transplantation), V9 (24 weeks \pm 7 days after transplantation). During the study, the vital signs, laboratory examinations, 12-lead electrocardiogram, chest HRCT, pulmonary functions, 6-minute walking distance, questionnaires, concomitant medications, adverse events, etc. will be checked and recorded.

Screening stage V1: After the patient signing the informed consent, relevant physical examination and check of previous physical examination will be done. The investigator will check inclusion and exclusion criteria, making judgement on whether the patient is eligible.

Cell collection stage V2: Tissue collection through bronchoscopy, cell isolation and expansion of around 4-8 weeks before autologous transplantation of REGEND001 autologous therapy product.

Baseline stage V3 (0-5 days before cell transplantation): 4-8 weeks later, conduct relevant examinations again and check inclusion and exclusion criteria. For idiopathic pulmonary fibrosis patients who are still eligible, they can formally join in this clinical trial and will receive autologous transplantation of REGEND001 cell products.

Cell transplantation stage V4 (the day of cell transplantation): According to the dose group each patient was assigned, a single administration of REGEND001 cell products at the corresponding dose were autologously transplanted to different lung segments through bronchoscopy. Investigator should be on site during the transplantation, confirming the dose, starting and stopping time of the transplantation, and recording correctly. Close observation of the patients in the outpatient or hospital for 2-4 hours after administration, and the investigator will determine when the patients can leave based on the tolerance of the patients. After leaving the hospital, the patients should return back to the research center as required for follow-up.

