14. 12-lead electrocardiogram: heart rate, PR interval, QRS complex, QT interval (uncorrected), corrected QT interval QTc (QT/RR^{1/2}), and an overall comment (normal, abnormality without clinical significance, abnormality with clinical significance, need more interpretation). The original electrocardiogram with signature will be stored in research center, the results of electrocardiogram examination are recorded on CRF or eCRF.

15. Lung function (ventilation, diffusion): height, weight, forced vital capacity (FVC), forced expiratory volume in 1 second (FEV1), ratio of FEV1 to FVC, diffusing capacity of the lungs for carbon monoxide (DLCO), alveolar ventilation (VA), the ratio of diffusing capacity of the lungs for carbon monoxide to alveolar ventilation (DLCO/VA). DLCO is measured with single-breath method. The examination results within 3 months before cell therapy can be accepted as the lung function test result at the baseline stage.

16. Idiopathic pulmonary fibrosis acute exacerbation: an acute, clinically significant respiratory deterioration without clear cause, acute worsening of dyspnea and decreased lung function, leading to respiratory failure or even death.

17. Patients should be checked again for inclusion at baseline stage. Results of myocardial enzyme spectrum, autoantibody test, lung cancer markers, serological examination for syphilis, HIV, HBV, HCV, and chest HRCT at the screening stage can be accepted.

18. If abnormality with clinical significance was reported when the patient withdraws in advance, the patient should be followed up until the recovery from the adverse events, reaching a stable status or other clear outcomes as required by the investigator

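### Note 15 lets a lung function test from before an acute exacerbation stand as the baseline of a patient who is suspended and later dosed under section 5.2

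*Protocol*

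**What the plan says.** Section 5.2 of the protocol deals with a patient who, between enrolment and dosing, "becomes unsuitable for cell therapy (e.g., acute exacerbation of the condition, occurrence of severe complications". If the investigators expect recovery, preparation is paused and the cells are frozen. After clearance, "Once the subject is medically cleared, they can directly proceed to the trial, reschedule the treatment time", and the site is to "use the cells for treatment after cell recovery, culturing, and testing". The same section says that "a subject can undergo a maximum of two baseline assessments to verify the inclusion criteria".

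Two notes to the flowchart in section 1.4 bear on what counts as baseline:

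- Note 15, on lung function: "The examination results within 3 months before cell therapy can be accepted as the lung function test result at the baseline stage".
- Note 17, on re-checking eligibility at the baseline stage, lists screening results that may be reused. The list ends "and chest HRCT at the screening stage can be accepted".

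The default in section 1.4 is that at V3, 0 to 5 days before transplantation, the site will "conduct relevant examinations again and check inclusion and exclusion criteria". Section 5.2 also mentions "a follow-up CT scan (due to disease requirements or treatment interval exceeding 8 weeks" when it describes how a patient may turn out to be unsuitable.

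**The concern.** Section 4 says there is no control group, so each patient's own baseline is the only comparator for the FVC, DLCO-sb and DLCO/VA changes in section 8.2. If the baseline predates an exacerbation and dosing follows it, lung function lost before REGEND001 was given is reported as change after REGEND001. Dose groups hold 3 to 6 patients, and section 1 intends the efficacy data to inform the dose for later studies, so one misplaced baseline can be visible in a group summary.

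A second consequence concerns the patient. The same old value can support the eligibility re-check before a bronchoscopic procedure, although lung function may since have fallen.

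This cannot be left to an analysis plan. An analysis plan can choose among tests that were done, but it cannot supply a lung function test after the event and before dosing if none was taken.

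**Working it through.** The protocol gives no figure to reproduce. The check sets the rules side by side, then does calendar arithmetic.

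**Step 1. Do the rules meet?**

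- Section 5.2 names acute exacerbation as a reason to suspend and allows later dosing. It does not ask for lung function to be repeated.
- Note 15 sets one condition, the age of the test at cell therapy. An intervening event does not cancel the allowance.
- Inclusion criterion (3) in section 2.2 ties the DLCO and FVC limits to tests dated relative to screening, not to dosing. A pre-event result can still satisfy it at the re-check.
- Section 8.2 defines the lung function endpoints as changes from baseline at 4, 12 and 24 weeks.

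So the text permits a pre-event FVC or DLCO as baseline.

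**Step 2. When does the 3-month limit allow it?**

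Inputs: the screening stage lasts 14 days (section 1.4), so a test taken in that stage precedes cell collection by s = 0 to 2 weeks. Culture takes c = 4 to 8 weeks (sections 1.4 and 5.2). Three months is 89 to 92 days, or 12.7 to 13.1 weeks.

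Age at planned dosing = s + c. Slack = 3 months − (s + c).

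| s (weeks) | c (weeks) | Age at planned dosing | Slack (weeks) |
|---|---|---|---|
| 0 | 4 | 4 | 8.7 to 9.1 |
| 0 | 8 | 8 | 4.7 to 5.1 |
| 2 | 4 | 6 | 6.7 to 7.1 |
| 2 | 8 | 10 | 2.7 to 3.1 |

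The slack, about 3 to 9 weeks, must hold both the time to clearance and the time to revive, culture and test the cells. The protocol gives no duration for either. A longer total delay takes the test outside the limit and forces a new one.

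The table assumes that the full culture time passed before suspension. Section 5.2 also covers partly cultured cells. Then c is shorter and the slack larger, though part of it goes on finishing the culture.

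**Step 3. How much can one patient move a group mean?**

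Shift = individual error / n, with n = 3 to 6 (section 1.3). The documents give no size for the error. As an assumption, take a lasting FVC loss across the event of 0, 100 or 200 mL:

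| Assumed loss (mL) | Shift, n = 3 | Shift, n = 6 |
|---|---|---|
| 0 | 0 | 0 |
| 100 | 100/3 = 33 | 100/6 = 17 |
| 200 | 200/3 = 67 | 200/6 = 33 |

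The shift makes the group look worse after treatment.

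**Step 4. HRCT.**

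Note 17 sets no age limit on the screening scan. However, section 6.7 makes HRCT part of diagnosing an exacerbation, and section 5.2 foresees a follow-up CT. A later pre-dose scan will therefore usually exist. What is missing is a statement that it replaces the screening scan as baseline.

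**The case against.** **The notes are permissive.** They are, and re-examination at V3 is the default. The error arises only if a site uses the allowance. A reader might infer that the protocol requires a pre-event baseline, or that a suspended patient skips the V3 check. It says neither. The flowchart rows for lung function and HRCT are missing from the text at hand, so what V3 schedules is known only from section 1.4 and the notes.

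**Other checks narrow the group.** Exclusions (7) to (9) in section 2.3 cover recent ventilation, recent pneumonia and long daily oxygen use, and section 5.2 leaves room for investigator judgement. If exclusion (19) bars anyone with a single exacerbation in the past year, the re-check stops this patient, and (19) then conflicts with the example in 5.2. If its threshold of three covers both kinds of event, the gap is open. The wording does not settle which. Under either reading, note 15 makes no exception for another respiratory deterioration.

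**HRCT is mostly covered.** This largely stands. A reader might infer that the screening scan must be the efficacy baseline and that the later state is lost. Note 17 is framed around the eligibility re-check and does not say so, and a scan made around the event will usually be available. It may date from the acute phase, and a merely suspected exacerbation may lack one.

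**The error is conservative, and the fix may flatter the product.** If recovery is incomplete at the new V3, later natural recovery would look like benefit. This caveat should be stated. It does not justify keeping a baseline from before the event: the last state before dosing is the proper reference for change after dosing, and the eligibility re-check needs a current value in any case.

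**Conclusion.** The point holds for lung function. Stated rules, not mere silence, allow an FVC or DLCO from before an exacerbation to be the baseline, and to support eligibility, of a patient dosed after it, whenever the added delay fits the remaining part of the 3 months. That the slack is about 3 to 9 weeks rests on a test taken during screening and a full culture before suspension.

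The consequence is limited. The case is rare, the allowance must actually be used, and the affected endpoints are secondary and descriptive. The size of the individual error is unknown, and the millilitre figures are only an illustration. A reader might infer that the dose decisions are compromised. They are not: the primary outcome in section 8.1 and the 28-day escalation rule in section 1.3 count adverse events and do not use these baselines.

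For HRCT the point is only a clarification of which existing scan is the baseline. Overall this is a cheap improvement that is worth making.

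**What to change.** Add to note 15: *This allowance does not apply to a patient suspended under section 5.2 for an acute exacerbation or other respiratory deterioration. For that patient, lung function is repeated at the final V3 after clearance, and the result is used both for the eligibility re-check and as the baseline.*

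Add to note 17: *For such a patient, the latest HRCT after the event and before dosing replaces the screening HRCT as baseline. A new scan is made only if none exists.*

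The cost is one routine, non-invasive lung function test, and rarely one HRCT with its radiation, in an uncommon patient. The remaining weakness is possible bias in favour of the product if recovery is incomplete at the new V3. The report should identify such patients and say so.

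Optionally, reword exclusion (19) so that it is clear whether the threshold of three applies to exacerbations as well as to hospitalisations. If a single exacerbation is meant to exclude, remove that example from section 5.2.
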